1.9 Rationale for Outcome Measures: Neuropsychological Assessment

Neuropsychological assessment plays a critical role in identifying and monitoring central nervous system (CNS) dysfunction in children with developmental, acquired, and medical disorders, including NF1. Objective standardized tests assessing general cognitive ability and specific neuropsychological domains are reliable and valid measures that are sensitive to changes in CNS function, including cognitive improvements from pharmacological treatments (e.g. Bedard, Martinus, Ickowicz & Tannock, 2004; Tucha, Mecklinger, Laufkotter, Klein, Walitza et al., 2006). As a result, neuropsychological test scores have been extensively used as cognitive outcome measures in clinical trials, including those with children (e.g., Bedard et al., 2004; Kempton, Vance, Maruff, Luk, Costin et al., 1999; Mehta, Goodyer & Sahakian, 2004; Mohr & Brouwers, 1991). When selecting neuropsychological tests to be used in clinical trials, various guidelines should be followed (Ruff & Crouch, 1991). First, tests should be selected that will assess the specific cognitive domains that are affected and may be changed by treatment. Second, as the tests need to be administered repeatedly, it is optimal that alternate forms be used where possible to minimize test-retest effects. Finally, the tests should be standardized measures with documented reliability and validity.

The selected measures in this study are drawn from both traditional pencil-and-paper neuropsychological tests as well as two computerized tasks which are sensitive to detecting treatment effects – the Cambridge Neuropsychological Testing Automated Battery (CANTAB, reviewed by Luciana, 2003) and the Conners' Continuous Performance Test-II (CPT-II; Conners, 2000). The CANTAB is a neuropsychological assessment battery that consists of 22 stand-alone subtests (we will administer 4 subtests only), developed to assess aspects of visual spatial learning, executive function, attention, semantic/verbal memory, decision making and response control. The CANTAB was selected as an outcome measure for a number of reasons. First, it has a number of subtests, including a visual spatial learning task that may potentially be

affected by Lovastatin. Second, the CANTAB has evolved from animal behavior paradigms to facilitate cross-species studies of cognition. As such, it has strong theoretical underpinnings. Third, it has been designed with a neural systems approach in mind, being extensively validated in patients with damage in specific areas of the brain. Fourth, it has extensive functional neuroimaging data available, outlining the neural substrates involved in many of the subtests, providing a useful confirmation of the neuroanatomical basis of the tests. Fifth, the tests are entirely computerized, enabling automatic recording of response accuracy and latencies via a touch-screen apparatus. This increases the consistency of data collection between sites. In addition, there are five equivalent forms available, minimizing retest practice effects. Subtests from the CANTAB start at a simple level and gradually increase in difficulty. Finally, research suggests that computerized batteries, in particular the CANTAB, are sensitive to subtle neurocognitive changes and may be better able to detect subtle cognitive dysfunction and changes over time than traditional paper-and-pencil neuropsychological measures (Bedard et al., 2004; Froestl, Gallagher, Jenkins, Madrid, Melcher et al., 2004; Makdissi, Collie, Maruff, Darby, Bush et al., 2001; Nestor, Scheltens & Hodges, 2004).

In this study, the primary outcome measures have been selected based on the effects of Lovastatin in murine models of NF1 and the cognitive functions that are frequently impaired in children with NF1. Therefore, the primary outcome measures assess visual spatial learning and sustained attention. Visual spatial learning will be assessed using the Paired Associate Learning (PAL) subtest from the CANTAB (see Section 5.1.4.1). Preliminary findings indicate that 46% (13/28) of children with NF1 performance on the PAL is impaired (>1SD below normative mean; Payne, Barton & North, unpublished data). Sustained attention will be assessed using the Score! subtest from the Test of Everyday Attention for Children (TEA-Ch). Previous findings indicate that 63% (50/80) of children with NF1 have impaired performance (>1SD below normative mean) on the Score! subtest (Hyman et al., 2005).

Since evidence from the murine model of NF1 suggests that Lovastatin may improve functions that rely on prefrontal cortex, such as response inhibition and the effect of Lovastatin on cognitive impairments is not known, a broader battery of neuropsychological tests have been included as secondary outcome measures. These include multidimensional measures of attention (selective, divided and switching attention from the TEA-Ch; see Hyman et al., 2003, 2005, 2006), executive functioning (e.g. response inhibition, planning and organization) and visuospatial ability, as well as quality of life.

The other computer-based measure, the CPT-II, has a significant history of use in identifying attentional deficits and the effects of stimulant medication (e.g., Boonstra, Kooij, Oosterlaan, Sergeant, & Buitelaar, 2005; Conners, Epstein, Angold, & Klaric, 2003). CPTs have been used in previous studies of children with NF1 (Ferner et al., 1996; Mautner et al., 2002; Mazzocco et al., 1995). Results from a recent study using the Kiddie's CPT, indicated that children with NF1 made significantly more omission (inattentive) errors than the control group (Irle, Shores, Watt & North, unpublished data).

1.10 Summary and Overview of Study

The most common neurological complication of NF1 in childhood is cognitive deficits for which there are no effective specific pharmacological treatments. Studies indicate that Lovastatin can reverse the biochemical, electrophysiological and cognitive deficits observed in *Nf1* +/- mice to levels comparable to wild-type control mice. *Nf1* +/- mice treated with Lovastatin demonstrated improved performance on tasks of spatial learning and memory (as measured by the Morris Water maze), attention, and pre-pulse inhibition. These tasks are hypothesized to reflect the cognitive deficits observed in children with NF1. The Morris Water Maze involves mechanisms of learning and memory, which relies on hippocampal functioning. While visual-spatial deficits have been reported in children with NF1 (e.g., Schrimsher, Billingsley, Slopis & Moore, 2003), no studies have reported on the visual spatial learning abilities in this cohort.

Lovastatin, which targets the inhibition of ras, is a logical choice as a potential therapeutic intervention for children with NF1 and cognitive deficits. Clinical trials indicate that Lovastatin is effective and safe to treat heFH in adults and children. Results from a recently completed Phase I trial indicate that Lovastatin is safe to be used in children (10-17 years) with NF1 (Acosta et al., submitted).

Currently, no studies have examined the effect of Lovastatin on cognitive functioning in individuals with NF1. This study will determine the efficacy of Lovastatin as a treatment for the cognitive deficits observed in children with NF1. We will conduct a multi-center randomized, double-blind, Phase II trial with two treatment arms (Lovastatin/placebo) for 16 weeks. Based on predictions from the NF1 murine mouse model, it is expected that children with NF1, who are impaired on a visual spatial learning task and/or an attention task, will benefit from Lovastatin.

2.0 Research Plan

2.1 Specific Aim

The specific aim of this study is to determine whether Lovastatin significantly improves visual spatial learning and/or sustained attention in children with NF1.

2.2 Secondary Aims

- 2.2.1. To evaluate the effect of Lovastatin on measures of executive function, behavior and quality of life in children with NF1 and cognitive deficits;
- 2.2.2. To further evaluate the toxicity and tolerability of Lovastatin in children with NF1 and cognitive deficits.

2.3 Hypotheses

It is hypothesized that Lovastatin will improve the visual spatial memory and/or attention deficits in children with NF1. This is based on studies demonstrating that Lovastatin has significantly improved impairments in visual spatial memory and attention in the NF1 murine model.

It is further expected that Lovastatin will be safe and well tolerated over a 16-week period.

3.0 Research Design and Methods

3.1 Study Design

This is a prospective multi-center; randomized, placebo-controlled Phase II study to determine the efficacy of Lovastatin on visual spatial learning and/or attention abilities of children with NF1 aged 8 to less than 16 years. In addition, the effect of Lovastatin on secondary measures of executive function, visual spatial skills, behavior and quality of life will be assessed. Participants will be randomized to 16-weeks of treatment with Lovastatin or a matched placebo. It is plausible and ethical to employ a placebo group as no standard therapy with established efficacy is being withheld. There is no cross-over in this study due to a lack of data concerning the length of possible washout effects. The Lovastatin dose will begin at 20 mg once daily/continuous dosing and escalate over a two-week period to 40 mg once daily/continuous dosing and continue at this dose for 14 weeks. Participants will be carefully monitored for side effects. The safety of Lovastatin will be evaluated using laboratory tests, clinical signs and adverse effects, which will be monitored at regular intervals over the 16-week period. Primary and secondary outcome measures will be administered at baseline, 16 weeks post-treatment and at follow-up, 8 weeks after cessation of treatment to determine any carry-over effects. The safety of Lovastatin will also be evaluated, with regular monitoring of side-effects during the trial.

4.0 Study Population

4.1 Human Subject Selection

This is a Phase II study involving children with NF1 (aged 8 years to less than 16 years at time of screening) with evidence of cognitive impairment, defined as having a score of at least one standard deviation or more below the population mean on a measure of visual spatial learning and/or attention.

A total of 142 participants with NF1 aged 8 years to less than 16 years will be enrolled in the study. The age limits were selected on the basis that Lovastatin has been shown to be safe and well tolerated in children aged between 10 and 17 years old. Lovastatin has been extensively used in children 10-17 years of age with hypercholesterolemia, with minimal side effects. Also, results from Phase 1 study indicate that Lovastatin is safe and well tolerated in children with NF1 aged 10-17 years (see section 1.4). Despite the lack of preliminary data in terms of safety using Lovastatin in children aged 8 and 9 years of age, we do not anticipate higher risk of side effects in this age group compared with children 10 years and older. During the phase 1 study (Acosta et al., submitted), 4 patients aged 10 years participated in the study. In all cases, no side effects or

significant changes in metabolic parameters were observed in this group compared with the older patients. In addition, metabolic pathways related to the metabolism of drugs, including Cytochrome P450 complex, are approximately developed up to 70% after the perinatal period (Lange, Pharmacology). It is considered fully developed by 5 years of age (Anderson et al 2009). Adjustments in the doses are related with changes in weight mainly. We do not expect changes in toxicity in this younger age group and those patients will be monitored closely as per study protocol during the study for immediate identification of any risk(s) or side effect(s).

In addition, one of the primary outcome measures (attention) only has normative data for up to 15 years 11 months. Therefore, the maximum age limit for participants at time of enrolment is 15 years 11 months so that normative data can be used to determine whether participants are impaired. The pediatric NF1 population is an ideal group in which to study the cognitive effects of Lovastatin because it represents an opportunity for early pharmacological intervention of cognitive deficits.

Participants will be recruited from the following sites*:

4.2 Inclusion Criteria

- Males or females aged between 8 years to less than 16 years at time of screening who meet NIH diagnostic criteria for NF1 (Appendix 1);
- Participants must have a full-scale IQ of 70 or above. In cases where there is a statistically significant difference between verbal IQ and performance IQ (.05 level as determined by Table B3 in the WASI manual), participants will be eligible if at least one of these quotients is 70 or above;
- Participants must have a cognitive impairment defined as having a score of at least one standard deviation or more below the population mean on one or more of the primary objective outcome measures (i.e., impaired on a measure of visual spatial learning and/or sustained attention);
- Participants must be medically stable;
- Participants who are on a stable dose of methylphenidate and/or dextroamphetamines for at least one month prior to screening and who will remain on the same dose for the duration of the study (see Section 4.3 for exclusion criteria regarding other psychotropic medication, i.e. medication capable of affecting the mind, emotions or behavior)
- Hepatic function: Participants must have adequate liver function defined as at least 3 of the 4 liver function tests to be $< 2 \times$ upper limit of normal for age according to institution standards (AST, ALT, Direct bilirubin, Indirect bilirubin [computed from total bilirubin and direct bilirubin]) and no tests should be $>5 \times$ upper limit of normal for age;
- Renal function: Participants must have adequate renal function defined as serum creatinine $\leq 1.5 \times$ upper limits of normal for age, and BUN $\leq 1.5 \times$ upper limits of normal for age or a creatinine clearance of greater than 70 ml/m/1.73m²;
- Hematologic function: Participants must have an absolute neutrophil count of $> 1,000$, a hemoglobin ≥ 10 gms/dl, and a platelet count $> 100,000$ on study entry;
- Participants must sign all required documents, including informed assent and HIPAA documents;
- Female participants of childbearing age should not be pregnant, must have a negative pregnancy test before initiation of treatment, and take appropriate birth control precautions to participate in this study.

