In another randomized double-blind trial, the efficacy, safety, and tolerability of Lovastatin was evaluated in 69 adolescent boys (9 to 17 years) with heFH (Lambert, Lupien, Gagne, Levy, Blaichman et al., 1996). Following a four-week placebo run-in period, the participants were randomized to receive active treatment with Lovastatin (10, 20, 30, or 40 mg/day) for eight weeks. Three children who received 30 or 40 mg/day of Lovastatin experienced transient AST elevations. A total of 10 children reported 13 adverse clinical events while receiving Lovastatin

including headache, fatigue, heartburn, jaundice, muscle cramps, chest pain, lymph node enlargement, and cold-and flu-like symptoms. Adverse events did not appear to be dose related (Lambert et al., 1996). There were no serious adverse experiences reported. None of the reported clinical adverse events or laboratory abnormalities required early withdrawal from the study.

In general, Lovastatin is considered a safe medication, and has been approved for the treatment of familial heFH in children 10 to 17 years old (Clauss et al., 2005; Stein et al., 1999). These studies, combined with results from the aforementioned Phase I study (Acosta et al., submitted), indicate that Lovastatin in doses of 40mg/day should be safe and well-tolerated in children with NF1.

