5.1.3 Laboratory Studies

A pre-treatment enrollment laboratory test will be performed at least two weeks prior to commencing the study medication. The following studies will be performed:

- Hematology: Complete blood count (CBC);
- Chemistries: Blood urea nitrogen (BUN), creatinine, alanine aminotransferase (ALT), aspartate aminotransferase (AST), CPK and, Lipid profile (HDL, Cholesterol, LDL, Triglycerides), total bilirubin and direct bilirubin (indirect bilirubin will be computed from total and direct bilirubin serum measurements);

- Urine Pregnancy Test: A urine pregnancy test will be performed on all females of childbearing age before commencing study medication and at weeks 8 and 16.

In order to ascertain an accurate lipid profile, participants will fast overnight before their laboratory tests are performed. This will apply to all lipid assessments conducted during the study period.

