5.2.3 Off-Study Criteria (Note: See Section 6.6 for modifications for toxicity information)

A participant will be taken off the study for the following reasons:

- The participant refuses further treatments and/or wishes to withdraw from the study;
- For participants concurrently taking stimulant medications (methylphenidate and/or dextroamphetamines), they will be withdrawn from the study if they stop or change the dose or type of stimulant medication before their final study visit;
- It is deemed in the best interest of the participant to stop the study by the research team;
- Serious protocol violation or non-compliance as determined by the principal investigator or research team;
- The development of significant drug toxicity, such as recurrent grade 3 or 4 toxicity after dose reduction; and/or persistent grade ≥ 2 toxicity for >10 days without administration of the drug;
- The development of a concurrent serious medical condition that might preclude or contraindicate the administration of Lovastatin;
- Death.

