6.6 Modifications for Toxicity

Participants who experience grade 2 toxicity related to Lovastatin will have Lovastatin withheld until the toxicity resolves (grade ≤ 1) and then restarted at the same dose level. If the grade 2 toxicity recurs, the dose will be withheld again until the toxicity resolves (grade ≤ 1) and then reduced to 50% of the dose. If the grade 2 toxicity recurs, the participant will be taken off the protocol. The participant will be evaluated by the principal investigator.

Participants who experience grade 3 or 4 toxicity related to Lovastatin will have their dose withheld. If the toxicity returns to grade ≤ 1 within 10 days, the participant may resume Lovastatin at a dose reduced by 50%. If the toxicity persists at grade ≥ 2 for >10 days without administration of Lovastatin or the grade 3 or 4 toxicity recurs at the lower dose, the participant will be removed from the study.

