All adverse events will be tabulated by treatment arm, severity grade and reported to the NF1 Data and Safety Monitoring Board (DSMB). The occurrence of adverse events will be reviewed by the DSMB at 2-month intervals to monitor patient safety. Summary details of the occurrences and grade of adverse events will be distributed to each site at 2-monthly intervals. It will be the responsibility of the site principal investigator to disclose this information to the site's institutional review board. In addition, all unexpected and serious adverse events will be forwarded to the medical monitor, [name]. She will serve as a patient advocate, will be independent of the clinical study team, and will report to the DSMB. She will oversee the progress of the protocol, especially issues of individual subject/patient management and safety. The monitor will provide an unbiased written report of each event.

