Headache	none	mild pain not interfering with function	moderate pain: pain or analgesics interfering with function, but not interfering with activities of daily living	severe pain: pain or analgesics severely interfering with activities of daily living	disabling
GASTRO-INTESTINAL					
Abdominal pain or cramping	none	mild pain not interfering with function	moderate pain: pain or analgesics interfering with function, but not interfering with activities of	severe pain: pain or analgesics severely interfering with activities of daily living	disabling

			daily living		
Constipation	none	requiring stool softener or dietary modification	requiring laxatives	requiring manual evacuation or enema	obstruction or toxic megacolon
Diarrhea participants without colostomy:	none	increase of <4 stools/day over pretreatment	increase of 4-6 stools/day, or nocturnal stools	increase of >7 stools/day or incontinence; or need for parenteral support for dehydration	physiologic consequences requiring intensive care; or hemodynamic collapse
Flatulence	none	mild	moderate	-	-
HEPATIC					
AST	WNL	>ULN - 2.5 x ULN	>2.5 - 5.0 x ULN	>5.0 - 20.0 x ULN	>20.0 x ULN
ALT	WNL	>ULN - 2.5 x ULN	>2.5 - 5.0 x ULN	>5.0 - 20.0 x ULN	>20.0 x ULN
Bilirubin	WNL	>ULN - 1.5 x ULN	>1.5 - 3.0 x ULN	>3.0 - 10.0 x ULN	>10.0 x ULN
MUSCLE					
CPK (creatine phosphokinase)	WNL	>ULN - 2.5 x ULN	>2.5 - 5 x ULN	>5 - 10 x ULN	>10 x ULN
Muscle weakness (not due to neuropathy)	normal	asymptomatic with weakness on physical exam	symptomatic and interfering with function, but not interfering with activities of daily living	symptomatic and interfering with activities of daily living	bedridden or disabling
Myositis (inflammation/damage of muscle) Also consider CPK. Note: Myositis implies muscle damage (i.e., elevated CPK).	none	mild pain, not interfering with function	pain interfering with function, but not interfering with activities of daily living	pain interfering with function and interfering with activities of daily living	bedridden or disabling
Myalgia (muscle pain)	none	mild pain not interfering with function	moderate pain: pain or analgesics interfering with function, but not interfering with activities of daily living	severe pain: pain or analgesics severely interfering with activities of daily living	Disabling

B. TIMETABLE

As outlined in the statement of work, the general timetable of this project is as follows:

0 – 12 weeks: Initiation of the study and subject recruitment

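### The entry limits for AST, ALT and CPK are looser than the grade 1 limit that section 6.6 requires before lovastatin can restart, so a child back at an accepted entry value can be kept off drug or removed

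*Protocol*

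**What the plan says.** **Entry.** Section 4.2 names four liver tests: AST, ALT, direct bilirubin and indirect bilirubin. At least three must be below 2 x ULN, and "no tests should be $>5 \times$ upper limit of normal for age". One of AST or ALT may therefore lie anywhere up to and including 5 x ULN. Section 4.3 refers back to these limits and adds none. Section 5.1.3 lists CPK among the pre-treatment chemistries ("aspartate aminotransferase (AST), CPK and, Lipid profile (HDL, Cholesterol, LDL, Triglycerides"), but no numeric CPK limit appears in 4.2 or 4.3.

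**Grades.** In Appendix 7, grade 1 ends at 2.5 x ULN for AST, ALT and CPK, and grade 2 ends at 5 x ULN. Grade 3 starts above 5 x ULN. Grade 4 starts above 20 x ULN for AST and ALT, and above 10 x ULN for CPK.

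**Actions.** For grade 2, section 6.6 says: "Participants who experience grade 2 toxicity related to Lovastatin will have Lovastatin withheld until the toxicity resolves", with resolution defined as grade 1 or lower. For grade 3 or 4, drug may resume at half dose if the grade falls to 1 or lower within 10 days. The removal clause begins "If the toxicity persists at grade ≥ 2 for >10 days without administration of Lovastatin". Section 5.2.3 has a matching off-study criterion ("toxicity for >10 days without administration of the drug"). Neither section mentions the value at entry.

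**The concern.** Eligibility and dose-modification rules should share a scale. Otherwise a value that was acceptable for starting drug becomes a bar to continuing it. Two things are at stake.

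- A child whose enzyme has returned to where it was at entry can be kept off drug, or removed, because of the entry value and not because of a remaining drug effect.
- With no CPK limit, lovastatin can be started in a child whose CPK is at a grade that would require withholding if it arose on drug and was judged related. Muscle toxicity is a listed risk: section 6.5.2 requires immediate discontinuation if myopathy is suspected.

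The protocol already aligns its haematology limits. Entry requires haemoglobin of at least 10 g/dL and platelets above 100,000, while grade 1 in Appendix 7 extends down to 10.0 g/dL and 75,000. The liver limits do not follow that pattern, and CPK has no limit.

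**Working it through.** The plan states no figure to reproduce, so the check sets the rules side by side.

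| Test | Highest value allowed at entry (4.2, 4.3) | Highest value for restart (6.6 with Appendix 7) | Gap |
|---|---|---|---|
| AST or ALT (one of them) | 5.0 x ULN | 2.5 x ULN | 5.0 / 2.5 = 2.0-fold |
| CPK | no numeric limit | 2.5 x ULN | unbounded |

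**Case A, grade 3 rise.** ALT is 4 x ULN at entry, with the other three liver tests below 2 x ULN, so the child is eligible. ALT rises to 6 x ULN (grade 3), is judged related, and drug is withheld. ALT returns to 4 x ULN, which is grade 2. Grade 1 is not reached within 10 days, and grade 2 persists beyond 10 days off drug. Section 6.6 requires removal although the child is back at the entry value.

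**Case B, grade 2 rise.** ALT is 3 x ULN at entry, rises to 4 x ULN, is judged related, and returns to 3 x ULN. This is still grade 2, so 6.6 does not permit restart. Its grade 2 paragraph has no 10-day limit, so 6.6 alone does not remove the child.

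**Case C, CPK at entry.** CPK is 6 x ULN before treatment, which is grade 3. No numeric criterion stops the child from starting.

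**Number of children.** The documents give no baseline distribution of AST, ALT or CPK, so the number cannot be calculated. For AST one can ask how common a grade 2 entry value would have to be before one affected child is expected. Inputs:

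- 142 / 2 = 71 children on lovastatin (section 7.0).
- 3 of 69 boys in the eight-week active-dose study in section 1.5 had AST rises: 3/69 = 4.3% (95% CI 0.9% to 12.2%). Cause and grade are not stated. The 69 covers all four doses, whereas the rises were at 30 or 40 mg.
- Assumptions: every such rise would be judged related, and rises are independent of the entry value.

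Expected number = 71 x p x rise rate, where p is the proportion entering with AST above 2.5 x ULN. Setting this to 1:

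- at 4.3%: p = 1 / (71 x 0.0435) = 1 / 3.09 = 32%;
- at the upper limit: p = 1 / (71 x 0.1218) = 1 / 8.65 = 12%.

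Attribution is made blind, so placebo children could also be caught. Counting them at the same rate halves these values to 16% and 6%. Section 1.4 reports all laboratory results within normal parameters in the 23 Phase I children with NF1. That study does not estimate p, but it gives no sign of values this high. The documents give no corresponding rates for ALT or CPK.

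**The case against.** **Clinical judgment covers most of this.** Section 6.6 acts only on toxicity judged related, so a stable entry elevation need not trigger it. Section 6.8 treats an adverse event as resolved at return to baseline, and Appendix 10 (UK sites) counts pre-existing conditions only if they worsen. Section 4.2 requires medical stability. Section 4.3 excludes neuromuscular disease and lets the investigator exclude a child whose unrelated illness would impair tolerance of the drug. This stands in part. However, the wording in 6.8 governs follow-up of events and that in Appendix 10 governs what counts as one. Neither overrides the explicit grade 1 condition in 6.6. Leaving it to judgment also lets sites treat identical children differently.

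**A stopping rule stricter than the entry rule errs toward safety.** That is a fair reason not to loosen 6.6. It does not explain why the entry limits are looser, and it does not help with CPK at the start of treatment.

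**Stronger readings that the documents do not support.**

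- A reader might infer that 5.2.3 forces the child in Case B off study. It is a removal rule, not a restart rule, and it is framed around significant drug toxicity that has developed. Whether a value back at entry level qualifies is a matter of reading.
- A reader might take "Three children who received 30 or 40 mg/day of Lovastatin experienced transient AST elevations" (section 1.5) as proof of drug-related rises at this dose. The text does not attribute them to drug, no placebo group was treated alongside, and no laboratory abnormality there required early withdrawal. The placebo-controlled study of 132 boys in the same section found no significant difference between groups in CPK or AST rises.
- A reader might turn the normal Phase I results into an upper bound on grade 2 entry values here. They concern any abnormal value in another sample and give no such prevalence.
- A reader might see a bias in the safety comparison, since "All adverse events will be tabulated by treatment arm, severity grade and reported to the NF1 Data and Safety Monitoring Board (DSMB". Randomization spreads raised entry values over both arms, so the effect on that table is at most noise.

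**Conclusion.** The mismatch is in the text and holds at MINOR severity. For one of AST or ALT, the entry ceiling is twice the restart ceiling. For CPK there is no entry ceiling. Section 6.6 as written requires removal in Case A and bars restart in Case B. In Case C only medical stability, the neuromuscular exclusion and the investigator's judgment under 4.3 stand between the child and the drug.

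Probably no child or one child would be affected. That is a judgment resting on the normal Phase I results and the AST arithmetic. It assumes that grade 2 entry values are uncommon and that rises are independent of them.

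It would go too far to infer a threat to the primary result. The analysis is intention-to-treat (section 7.0). Section 5.3 still tests children withdrawn early if at least four weeks have passed since baseline, unless the reason is non-compliance.

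Bilirubin is only a point to clarify. Appendix 7 grades a single bilirubin entry, with grade 3 at ">3.0 - 10.0 x ULN", and does not say whether total, direct or indirect is meant. Whether the same gap exists there cannot be settled from the documents.

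**What to change.** In section 4.2, require AST, ALT and CPK each to be 2.5 x ULN or less at entry, which is grade 1 or lower in Appendix 7. The 5 x ULN ceiling then matters only for bilirubin, and the withholding, restart and removal rules in 6.6 work as written. State in Appendix 7 which bilirubin is graded.

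The cost is a short amendment to 4.2 and one clarifying line. All three tests are already in the pre-treatment panel. A few children may be excluded or need a repeat test.

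The alternative is to keep the 5 x ULN limit and let 6.6 accept a return to the entry grade. That would restart a statin above 2.5 x ULN and would still need a CPK entry limit, so tightening 4.2 is preferable.
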